7. DISCONTINUATION OF STUDY INTERVENTION AND PARTICIPANT DISCONTINUATION/WITHDRAWAL

7.1. Discontinuation of study intervention

Discontinuation of study intervention refers to any participant who has not received all planned doses of the study intervention. In rare instances, it may be necessary for a participant to permanently discontinue study intervention. If study intervention is permanently discontinued, the participant should, if possible, continue other study procedures (e.g., safety or immunogenicity), planned in the study protocol at the discretion of the investigator.

The primary reason for premature discontinuation of the study intervention will be documented in the eCRF based on the list below:

Reasons	Additional items/Sub-reasons
AE	Unsolicited AE
	Solicited AE
	SAEs / pIMDs /AESIs
Lost to follow-up	
Withdrawal by Participant	Burden of Procedure
	Participant Relocated
	COVID-19

Reasons	Additional items/Sub-reasons
	Other, Specify
Investigator Decision	Specify
Protocol Deviation	Specify
Site Terminated by Sponsor	
Study Terminated by Sponsor	
Pregnancy	
Death	
Other	Specify

AE = Adverse event; AESI = Adverse event of special interest; COVID-19 = Coronavirus disease; pIMD = Potential immune-mediated disease; SAE = Serious adverse event.

7.1.1. Contraindications to subsequent study intervention administration

The eligibility for subsequent study intervention administration must be confirmed before administering any additional dose.

Participants who meet any of the criteria listed below or criteria listed in Sections [5.2.1](#) and [5.2.2](#) should not receive additional doses of study intervention. Such participants should be encouraged to continue other study procedures, at the investigator's discretion. All relevant criteria for discontinuation of study intervention administration must be recorded in the eCRF.

- Participants who experience any SAE judged to be possibly or probably related to study intervention or non-study concomitant vaccine/product, including hypersensitivity reactions.
- Participants who develop any new condition which, in the opinion of the investigator, may pose additional risk to the participants if they continue to participate in the study.
- Anaphylaxis following the administration of study intervention.
- Condition that in the judgment of the investigator would make intramuscular injection unsafe.
- Occurrence of a new pIMD or the exacerbation of an existing pIMD that, in the opinion of the investigator, expose the participant to unacceptable risk from subsequent vaccination. In such cases, the investigator should use their clinical judgment prior to administering the next dose of the study intervention. Refer to Section [8.4.4.1](#) for the definition of pIMD.
- Occurrence of a new AESI or the exacerbation of an existing AESI that, in the opinion of the investigator, exposes the participant to unacceptable risk from subsequent doses of study intervention. Refer to Section [8.4.4](#) for the definition of AESI.

- Pregnant or lactating female participant (Refer to Section 8.4.6).

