5.2.1. Medical conditions

- History of any reaction or hypersensitivity likely to be exacerbated by any component of the study intervention (For details on components of study intervention administered, refer to [Table 8](#) and *Arexvy SmPC/Prescribing information* [[Arexvy Summary of Product Characteristics](#), 2023; [Arexvy Prescribing Information](#), 2023]).
- Acute or chronic clinically significant cardiovascular or hepatic functional abnormality as determined by physical examination or laboratory screening tests.
- Recurrent or uncontrolled neurological disorders or seizures. Participants with medically controlled chronic neurological diseases can be enrolled in the study as per investigator assessment, provided that their condition will allow them to comply with the requirements of the protocol (e.g., completion of the diary cards, attend study site visits). Study participants may decide to assign a caregiver to help them complete some of the study procedures (Refer to [Section 8](#)).
- Any history of dementia or any medical condition that moderately or severely impairs cognition.

Note: If deemed necessary for clinical evaluation, the investigator can use tools such as Mini-Mental State Exam, Mini-Cog or Montreal Cognitive Assessment (to determine cognition levels of the participant).

- Any condition which, in the judgment of the investigator, would make IM injection unsafe.
- Significant underlying illness that in the opinion of the investigator would be expected to prevent completion of the study (e.g., life-threatening disease likely to limit survival up to study end).
- Acute disease and/or fever at the time of study intervention administration. Fever is defined as temperature $\geq 38^{\circ}\text{C} / 100.4^{\circ}\text{F}$ determined by oral or axillary route. However, participants with a minor illness (such as mild diarrhea, mild upper respiratory infection) without fever may be enrolled at the discretion of the investigator.
- Bedridden participants.

- Any other clinical condition that, in the opinion of the investigator, might pose additional risk to the participant due to participation in the study.

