5.2.2. Prior/Concomitant therapy

- Use of any investigational or non-registered product (drug, vaccine, or medical device) other than the study intervention administration during the period beginning 30 days before the first dose of study intervention administration (Day -30 to Day 1), or their planned use during the study period (up to Visit 6).
- Previous vaccination with the same antigen (RSV) containing vaccine as that of the study intervention, including investigational RSV vaccines.
- Planned or actual administration of a vaccine not foreseen by the study protocol in the period starting 30 days before the first dose of study intervention administration and ending 30 days after the last dose of study intervention administration*. In the case of COVID-19 and inactivated/subunit/split influenza vaccines, this time window can be decreased to 14 days before and after each study intervention administration.

**If emergency mass vaccination for an unforeseen public health threat (e.g., a pandemic) is recommended and/or organized by the public health authorities outside the routine immunization program, the time period of 30 days described above can be reduced, if necessary for that vaccine, provided it is used according to the local governmental recommendations and that the Sponsor is notified.*

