5.5. Criteria for temporarily delaying enrollment/ administration of study intervention

Enrollment/study intervention administration may be postponed within the permitted visit interval until transient conditions cited below are resolved and before the end of recruitment period:

- Participants (SOT patients) with any clinically significant (in the opinion of the investigator) hematologic/biochemical values out of normal range which are expected to be temporary may be retested once at a later date within the allowed visit interval.
- Acute disease and/or fever at the time of study intervention administration. Refer to the SoA (Section 1.3) for definition of fever and preferred location for measuring temperature in this study.
- Participants with a minor illness (such as mild upper respiratory infection, mild diarrhea) without fever may be enrolled and/or dosed at the discretion of the investigator.
- In case of administration of vaccines, study intervention administration should be postponed, within given protocol timelines and prior to the end of the study enrollment period, to allow respect of at least 30 days interval between other vaccination and study intervention administration.
- In case of administration of inactivated, subunit and split influenza vaccines or COVID-19 vaccines (fully licensed or with EUA): postponement of study intervention administration within given protocol timelines and prior to the end of the study enrollment period, to allow respect of at least 14 days interval between flu/COVID-19 vaccination and study intervention administration.
- Participants with symptoms suggestive of active COVID-19 infection (e.g., fever, cough, etc.). The return of the participant to the site will follow the specific guidance from local public health and other competent authorities (e.g., free of symptoms, COVID-19 negative testing, etc.).

- Participants with known COVID-19 positive contacts may be dosed at least 14 days after the exposure, provided that the participant remains symptom-free, and at the discretion of the investigator.

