9.2.1. Criteria for elimination from analysis

If the participant meets one of the criteria mentioned below or ones listed in the Section 7.1.1 (contra-indication to subsequent vaccination) or 5.2.1 (medical conditions) or 5.2.2 (concomitant therapy), he/she may be eliminated from per protocol analysis.

In case of administration of any medication mentioned in Section 5.2.2 during the study, this will be considered as a protocol deviation and the participant may be eliminated from the PPS.

Participants may be eliminated from the PPS for immunogenicity if, during the study, they incur a condition that has the capability of altering their immune response (intercurrent medical condition) or are confirmed to have an alteration of their initial immune status. Refer to [Definition of Terms](#) for the definition of intercurrent medical conditions.

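### Section 7.1.1 bars any further dose for conditions that Section 5.5 only postpones, so dose 2 in RSV_IC_2, and with it a co-primary value, can depend on which section a site follows

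*Protocol*

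**What the plan says.** Section 7.1.1 of the protocol sits under Section 7.1, on discontinuation of study intervention. Besides its own list, it refers to two sets of exclusion criteria: participants who meet "criteria listed in Sections [5.2.1](#) and [5.2.2](#) should not receive additional doses of study intervention". They are encouraged to continue other study procedures, and "All relevant criteria for discontinuation of study intervention administration must be recorded in the eCRF".

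Two of the imported criteria matter here. Section 5.2.1 lists "Acute disease and/or fever at the time of study intervention administration". Section 5.2.2 lists planned or actual use of a non-study vaccine inside a window opening "30 days before the first dose of study intervention administration and ending 30 days after the last dose of study intervention administration"; for COVID-19 and certain influenza vaccines this can be cut to 14 days either side of each dose.

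Section 5.5 handles the same conditions differently: "Enrollment/study intervention administration may be postponed within the permitted visit interval until transient conditions cited below are resolved". Its list repeats the acute disease and fever wording of Section 5.2.1. For other vaccines it tells the site to postpone "to allow respect of at least 30 days interval between other vaccination and study intervention administration", or 14 days for influenza and COVID-19 vaccines. Sections 8.1.5 and 8.1.6 say that the visit is rescheduled when health on the dosing day temporarily precludes dosing, and 8.1.6 says the same for fever.

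Table 2 requires both the Section 7.1.1 check and the Section 5.5 check at Visit 3. Section 9.2.1 names Sections 7.1.1, 5.2.1 and 5.2.2 as grounds on which "he/she may be eliminated from per protocol analysis"; it does not mention 5.5.

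**The concern.** At Visit 3 a site can meet one condition with two stated consequences: no further dose, or a dose later in the interval. No passage ranks the sections, and Section 8 rules out waivers.

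Only RSV_IC_2 has a second dose. Both co-primary endpoints are the MGI of Visit 4 over Visit 3 in that group, analysed on the PPS. A patient barred under Section 7.1.1 has no post-Dose 2 titer and drops out of the primary analysis. A patient postponed under Section 5.5 can contribute. Part of the primary analysis set could therefore depend on how a site reads the protocol.

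The broad cross-reference also brings in criteria that make sense only at study entry, such as "Previous vaccination with the same antigen (RSV) containing vaccine as that of the study intervention". That suggests the Section 5.2 lists were imported whole, without being checked for use before a second dose.

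**Working it through.** **Side-by-side reading at Visit 3 in RSV_IC_2**

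- *Non-study vaccine between doses, not influenza or COVID-19.* Suppose it is given 20 days after Visit 1. Under Section 5.5, dosing waits 30 days: 20 + 30 = 50 days after Visit 1, inside the 30–60 day interval of Table 5, so dose 2 may be given. In general, any such vaccine up to 60 − 30 = 30 days after Visit 1 can be accommodated. Under Section 5.2.2, the window runs from 30 days before the first dose to 30 days after the last. Day 20 lies inside it whether dose 1 or dose 2 counts as last, and waiting does not change that. Section 7.1.1 therefore bars dose 2 where Section 5.5 allows it. The one stated relaxation is the footnote on emergency mass vaccination.
- *Influenza or COVID-19 vaccine.* Sections 5.2.2 and 5.5 both use 14 days. Once 14 days have passed the two agree. Inside the 14 days, 7.1.1 says no additional dose and 5.5 says postpone.
- *Fever or acute disease.* The wording in 5.2.1 and 5.5 is the same and refers to the time of administration. On the day itself both sections stop the dose. They differ on what follows: 7.1.1 treats the criterion as discontinuation, while 5.5 and 8.1.6 reschedule.

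**The plan's own figures**

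Inputs from Sections 9.5 and 9.5.1: 100 evaluable, 20% attrition, 1-sided alpha 2.5%, SD of paired log10 differences 0.5 or 0.4.

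Enrolment: 100 / (1 − 0.20) = 125, as stated.

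Power of the paired t-test = 1 − F(t; n − 1, λ), where F is the noncentral t distribution function, t is the 97.5% point of t with n − 1 degrees of freedom, and λ = log10(fold) × √n / SD. For a 1.39-fold increase with SD 0.5 and n = 100, λ = 0.1430 × 10 / 0.5 = 2.86 and power is 80.9%. Solving for the fold gives 1.385 and 1.458 (SD 0.5; 80% and 90% power) and 1.298 and 1.352 (SD 0.4). Table 21 states 1.39, 1.46, 1.30 and 1.35, so it reproduces.

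**Illustration of size**

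The documents give no rate of transient conditions or between-dose vaccination at Visit 3. Purely as an assumption, take 3–8% of 125: 125 × 0.03 = 3.75 and 125 × 0.08 = 10, so about 4 to 10 patients. Against the allowance of 125 − 100 = 25, that is 4/25 = 16% to 10/25 = 40%.

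If such losses came on top of the planned attrition (SD 0.5):

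- 100 evaluable: power at 1.39-fold 80.9%; fold detectable at 80% power 1.385
- 95 evaluable: 78.8%; 1.397
- 90 evaluable: 76.6%; 1.410

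If the allowance absorbed them, the evaluable number would stay at 100 and nothing would change.

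**The case against.** The best defence is that the protocol already handles fever. The Section 5.2.1 criterion is tied to the moment of dosing, so a recovered patient no longer meets it. Section 8.1.6 says the visit is rescheduled and points to 5.5. Table 2 has a separate row for temporary delay at Visit 3, and its footnote b provides for resampling if dosing is delayed. Section 7.1.1 never calls the bar permanent, and Section 7.1 describes permanent discontinuation as rare. Most of this stands, and it makes fever the weaker part of the point. What remains is that 7.1.1 says none of it and is framed as discontinuation.

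The vaccination conflict is narrow. Table 10 already prohibits such vaccines between doses, and a patient who receives one may lose PPS status under Section 9.2.1 on either reading. That limits its effect on the primary analysis but does not settle whether dose 2 is given.

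The plan is also one of estimation without hypothesis testing, and the MGI is a within-participant measure in one group. Unequal loss between groups therefore does not by itself bias it.

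Two stronger readings are tempting and should not be drawn. A reader might infer that the previous-RSV-vaccination criterion bars dose 2 for the whole arm. The protocol expressly schedules two doses for RSV_IC_2 (Sections 4.1, 6.1 and 6.3.2, and Table 2), so this is a sign of loose cross-referencing and not an expected loss. A reader might also infer that a patient postponed for fever and dosed after recovery is removed from the PPS. That patient had no fever at dosing, and Section 9.2.1 makes elimination only possible.

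**Conclusion.** The inconsistency is in the current text. For a non-study vaccine other than influenza or COVID-19 given between doses, Sections 7.1.1 and 5.5 lead to opposite dose 2 instructions that waiting cannot reconcile. For fever, acute illness and influenza or COVID-19 vaccines, the sections can be read together, but only by supplying a qualification that 7.1.1 lacks.

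It affects dose 2 in RSV_IC_2, the group that carries both co-primary endpoints. The number of patients affected cannot be derived from the documents; the 3–8% range is an assumption with no source in them. On the plan's SD of 0.5, even 10 extra losses from 100 evaluable would cost about 4 percentage points of power (80.9% − 76.6% = 4.3), so the statistical cost is likely modest. No stated sample size figure is wrong. This should be fixed as a wording inconsistency; it does not undermine the design.

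**What to change.** Reconcile Sections 7.1.1, 5.2.1, 5.2.2, 5.5 and 8.1.6 so that each criterion checked at Visit 3 has one stated consequence: no further dose, or postponement within the interval. Which applies to each criterion is for the sponsor's clinical team to decide.

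In Section 7.1.1, replace the blanket reference to 5.2.1 and 5.2.2 with the specific criteria meant, so that entry-only criteria are no longer imported, and state how the section relates to 5.5. Then align the PPS elimination grounds in Section 9.2.1 with the reconciled list.

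The cost is protocol wording and a clarification letter to sites, with no new procedures, visits or patients.

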7.2. Participant discontinuation/withdrawal from the study

A participant may withdraw from the study at any time at the participant's own request for any reason (or without providing any reason).

A participant may be withdrawn at any time at the discretion of the investigator for safety, behavioral, or compliance reasons.

Investigators will attempt to contact participants who do not return for scheduled visits or follow-up.

All data and samples collected up to and including the date of withdrawal of/last contact with the participant will be included in the study analyses. If the participant withdraws consent for disclosure of future information, the sponsor may retain and continue to use any data collected before such a withdrawal of consent.

A participant can request for the destruction of their samples any time during the study. The investigator must document the request in the site study records. If a participant withdraws from the study, any samples taken and not tested, should not be tested, and should be destroyed, if applicable, as per local regulations.

The primary reason for participant discontinuation/ withdrawal from the study will be documented in the eCRF based on the list below:

Reasons	Additional items/Sub-reasons
AE	Unsolicited AE
	Solicited AE
	SAEs / pIMDs /AESIs
Lost to follow-up	
Withdrawal by Participant	Burden of Procedure
	Participant Relocated
	COVID-19
	Other, Specify
Investigator Decision	Specify
Protocol Deviation	Specify
Site Terminated by Sponsor	
Study Terminated by Sponsor	
Pregnancy	
Death	
Other	Specify

AE = Adverse event; AESI = Adverse event of special interest; COVID-19 = Coronavirus disease; pIMD = Potential immune-mediated disease; SAE = Serious adverse event.

Participants who are withdrawn from the study because of AEs/SAEs must be clearly distinguished from participants who are withdrawn for other reasons. Investigator will follow participants who are withdrawn from the study due to an AE/SAE/AESI until the event is resolved, stabilized, otherwise explained, or the participant is lost to follow-up (see Section 10.3.5.5).

7.3. Lost to follow-up

A participant will be considered lost to follow-up if the participant repeatedly fails to return for scheduled visits and is unable to be contacted by the study site.

The following actions must be taken if a participant fails to return to the clinic for a required study visit:

- The site must attempt to contact the participant/caregiver and reschedule the missed visit as soon as possible, within the allowed visit interval, counsel the participant on the importance of maintaining the assigned visit schedule and ascertain whether the participant wishes to and/or should continue in the study.
- Before a participant is deemed lost to follow-up, the investigator or designee must make every effort to regain contact with the participant/caregiver (where possible, 3 telephone calls, and if necessary, a certified letter to the participant's last known mailing address or local equivalent methods). These contact attempts should be documented in the participant's medical record.
- Should the participant continue to be unreachable, the participant will be considered to have withdrawn from the study.
- Site personnel, or an independent third party, will attempt to collect the vital status of the participant within legal and ethical boundaries for all participants randomized, including those who did not get study intervention. Public sources may be searched for vital status information. If vital status of the participant is determined as deceased, this will be documented and the participant will not be considered lost to follow-up. Sponsor personnel will not be involved in any attempts to collect vital status information.

8. STUDY ASSESSMENTS AND PROCEDURES

- Study procedures and their timing are summarized in the SoA (Section 1.3). Protocol waivers or exemptions are not allowed.
- Adherence to the study design requirements, including those specified in the SoA, is essential and required for study conduct.
- Immediate safety concerns should be discussed with the sponsor as soon as they occur or when the study team becomes aware of them. In case of doubts of immediate safety concerns regarding the inclusion of a possible participant, inclusion should be postponed until a decision can be made.

- All screening evaluations must be completed and reviewed to confirm that potential participants meet all eligibility criteria. Subjects who have signed informed consent but are not eligible to proceed should be recorded in the eCRF with a status of 'screen failure'. The investigator will maintain a log of all participants screened. All relevant information, such as confirmation of eligibility and reasons for screening failure will be mentioned in this screening log.
- Procedures conducted as part of the participant's routine clinical management (e.g., blood count) and obtained before signing of the ICF, and those conducted during the entire duration of the study may be utilized for screening or baseline purposes, as well as for safety follow-up (e.g., SoC tests to assess occurrence of allograft rejection in SOT patients) provided the procedures met the protocol-specified criteria and were performed within the timeframe defined in the SoA.
- Study participants may decide to assign a caregiver to help them complete the study procedures. Please refer to the [Definition of Terms](#) for the definition of a caregiver.
 - A caregiver can be appointed by the participant at any time during the study, when the participant feels it is necessary. Caregiver should receive the caregiver information letter before providing support to the study participant. Ideally, a single caregiver should be appointed by the participant but, in some situations, it may happen that several caregivers will support a study participant throughout the conduct of the study. This should be recorded in the source documents. However, every effort should be done to ensure that only one caregiver enters the data into the paper diary to allow for timely completion.
 - Caregivers may help the study participants with performing some practical study procedures such as receiving or making phone calls to site staff, planning study visits, transcribing responses to diaries, transportation to and from the study site etc. However, at no time, the caregiver should evaluate the participant's health status while answering diaries or make decisions on behalf of the participant. At the first study visit, the site staff should inform the participant of the possibility to appoint a caregiver. Then at subsequent study visit(s), the site staff should check again with the participants if they wish to appoint a caregiver or if there were or will be changes of caregiver.
- In the event of a significant study-continuity issue (e.g., caused by a pandemic), alternate strategies for participant visits, assessments, study intervention distribution and monitoring may be implemented by the sponsor or the investigator, as per local health authority/ethics requirements.
- It is preferred to have all visits on-site. However, during special circumstances (e.g., COVID-19 pandemic, SOT patients in whom health has deteriorated during the study, or for whom the transfer to the clinic has become very difficult), the specific guidance from local public health, if applicable, and other competent authorities regarding the protection of individuals' welfare must be applied and consulted with the sponsor. For the duration of such special circumstances, the following measures may be implemented for enrolled participants:

- Follow-up visits (Visit 3 in HA and IC 1-dose groups, and Visits 2, 4, 5, and 6 for all groups) may be conducted at the participant's home (by the site staff or by a home care service system), if appropriate. If home visits are not possible, telephone calls or other means of virtual contacts may be used.
- Diary cards may be transmitted from and to the site by electronic means or courier service if allowed by local regulations and or conventional mail or collected at home. Biological samples may be collected at participant's home. Biological samples should not be collected if they cannot be processed in a timely manner or appropriately stored until the intended use. Home Visits are not allowed for participants in the CMI subset (due to time-sensitivity of CMI samples) except in special circumstances and with the prior approval of the GSK central study team.
- Impact of visits performed outside of the site's location on the PPS for immunogenicity will be determined on a case-by-case basis.
- The maximum amount of blood collected from each participant over the duration of the study, related to procedures in this study, will not exceed 288 mL. Repeat or unscheduled samples may be taken for safety reasons or for technical issues with the samples.

